2.2 Overview of Nonclinical Studies

AK002 is a humanized non-fucosylated immunoglobulin G1 (IgG1) monoclonal antibody directed against the inhibitory receptor Siglec-8, a member of the CD33-related family of Siglecs.

Siglec-8 has a restricted tissue distribution, expressed selectively on the surface of mature eosinophils and mast cells, but not in early precursors of these cell populations. In blood, binding of AK002 to Siglec-8 induces ADCC against eosinophils, leading to rapid and sustained depletion of these cells from circulation. In the tissue, AK002 induces direct apoptosis of eosinophils and inhibition of mast cells. This profile of activity may provide clinical benefit in diseases in which these cell types play a role, such as eosinophilic gastritis and eosinophilic duodenitis.

Siglec-8 is not expressed in species other than humans, and therefore, 2 novel mouse models have been developed for *in vivo* testing of AK002. AK002 has been studied in Siglec-8 humanized and transgenic mouse models and with human blood and tissue cells. The first model uses immunodeficient mice capable of generating human immune cells including mast cells and eosinophils when engrafted with human hematopoietic stem cells. The ability of anti-Siglec-8 antibodies to inhibit mast cell-mediated reactions has been evaluated in this model. The second rodent model is a transgenic mouse line that expresses human Siglec-8. The expression of Siglec-8 on the cell surface in these mice is restricted to eosinophils, mast cells, and basophils, a pattern of surface expression equivalent to that in humans. Anti-Siglec-8 antibodies can prevent IgE-mediated anaphylaxis in this transgenic mouse line, indicating that Siglec-8 is pharmacologically active in the model. The ability of AK002 to effect mast cells and eosinophils has been evaluated in this model.

AK002 inhibits IgE-mediated mast cell degranulation and release of the newly formed mediator prostaglandin D2 in vitro without affecting mast cell viability. In peripheral blood preparations from normal human donors, AK002 shows selective depletion of eosinophils. Importantly, in a whole-blood cytokine-release assay using immobilized AK002 to enhance the potential for antibody crosslinking, AK002 did not lead to dose-dependent release of pro-inflammatory cytokines.

To evaluate the in vivo activity of anti-Siglec-8 antibodies in an immunocompetent rodent model, a transgenic mouse strain has been developed that selectively expresses human Siglec-8 on the surface of mouse mast cells, eosinophils, and basophils. In single-dose and repeat-dose studies in Siglec-8 transgenic mice, AK002 demonstrated selective depletion of peritoneal mast cells and circulating and tissue (spleen) eosinophils and basophils.

In 2 Good Laboratory Practice (GLP) toxicity and toxicokinetic studies, AK002 was well tolerated at doses of 50 mg/kg and 100 mg/kg, 5-fold and 10-fold, respectively, the level of the highest dose proposed to be studied in humans. AK002 showed sustained systemic exposure in Siglec-8 transgenic mice with an extended terminal half-life estimated as 272 hours or 337 hours following single IV administration of 50 mg/kg or 100 mg/kg, respectively. There was no evidence of anti-drug antibodies (ADA) in either study. Decreases in eosinophil counts in both sexes were observed, which reflect the expected pharmacology of AK002. The no-observed-adverse-effect level (NOAEL) following IV administration of AK002 to transgenic mice was 100 mg/kg, which supports the Phase 1 studies in humans.

2.3 Overview of Clinical Studies

AK002, administered as an intravenous infusion has been previously tested in healthy volunteers and in patients with indolent systemic mastocytosis (ISM), chronic urticaria (CU), severe allergic conjunctivitis (AC), mast cell gastritis, and eosinophilic gastritis (EG) and/or eosinophilic duodenitis (EoD), which was referred to as eosinophilic gastroenteritis (EGE) in previous studies.

Multiple doses of 3 mg/kg have been given to patients with ISM, CU, severe AC, EG, and/or EoD. In these studies, patients reported improvements in disease symptoms with AK002 pharmacodynamic (PD) activity being observed for prolonged periods of time and AK002 pharmacokinetic (PK) parameters demonstrating a half-life amenable to administration every 4 weeks.

To date, healthy volunteers and patients with ISM, CU, severe AC, EG/EoD, eosinophilic esophagitis (EoE), and mast cell gastritis have been enrolled in clinical studies. In general,

AK002 has been well tolerated. The most common treatment-emergent adverse event (TEAE) observed was infusion-related reaction (IRR). Most IRR were mild to moderate and resolved on their own, with no treatment required. Infusion-related reactions that were serious resolved within approximately 24 hours. Common symptoms of IRR were headache, nausea, sweating, flushing, and redness. Most IRR occurring during the infusion could be managed by slowing or temporary interruption of the infusion, with minimal intervention. In 6 healthy volunteers who received 2 doses of 0.3 mg/kg AK002, 4 weeks apart, the second dose was better tolerated than the first dose. This is also the case in patients with ISM, CU, severe AC, and EG/EoD with fewer adverse events (AE) reported during the second and subsequent infusions when compared to the first infusion.

In all studies there was a transient decrease in lymphocyte count after the AK002 infusion (usually resolving within 1 day) that was not associated with any clinical consequence and a sustained suppression of eosinophils that was consistent with the mechanism of action of AK002. No significant trends were observed for changes in vital signs, electrocardiograms (ECG), clinical laboratory parameters, or physical examinations.

In the randomized, double-blind, placebo-controlled, Phase 2 study of AK002 in 65 patients with EG and/or EoD, patients were randomized to receive monthly doses of placebo, low dose AK002 (0.3, 1, 1, and 1 mg/kg), or high dose AK002 (0.3, 1, 3, and 3 mg/kg) in a 1:1:1 ratio (Dellon, 2020). All primary and secondary endpoints were met in the study. There was a 97% and 92% mean reduction in eosinophils in the stomach/duodenum for the high dose and low dose AK002-treated patients, respectively, versus a 10% increase for placebo-treated patients ($p<0.0001$). The reduction of eosinophils was associated with a statistically significant reduction in total symptom score (TSS) of 58% in the high dose AK002 group and 49% reduction in the low dose AK002 group versus a 24% reduction in the placebo group ($p=0.0012$ and $p=0.015$, respectively). Improvement in symptoms was observed within 24 hours of the first dose of study drug. In addition, 70% of high dose treated patients and 68% of low dose treated patients were treatment responders (defined as $>30\%$ improvement in TSS and $>75\%$ reduction from baseline in tissue eosinophils) versus 5% for placebo-treated patients ($p<0.0001$).

Approximately 40% of patients had concomitant EoE. In those patients, a mean reduction of 95% of eosinophils/hpf in esophageal biopsies for AK002-treated patients was observed versus no change for placebo-treated patients. Also, 13 of 14 AK002-treated patients (93%) were histologic responders as defined by ≤ 6 eosinophils/hpf versus 1 of 9 placebo-treated patients (11%). Dysphagia improved by 53% in AK002-treated patients versus 17% in placebo-treated patients.

More than 90% of patients in the Phase 2 study elected to continue into a long-term continuation study. In that study, a starting dose of 1 mg/kg AK002 was used, followed by subsequent doses of 3 mg/kg AK002. Premedication of 80 mg prednisone was administered the day before the first dose and second dose for 20 of the 58 patients dosed. Using this premedication regimen, no IRR were observed on the first infusion of the extension study.

A total of 38 patients have been treated for at least 72 weeks in the AK002-003X extension study. The drug has been well tolerated, and no consistent long-term drug related AE have been noted.

2.4 Eosinophilic Gastrointestinal Disorders

Eosinophilic gastrointestinal disorders (EGID) are chronic inflammatory disorders characterized by infiltration of eosinophils along different segments of the gastrointestinal tract, in the absence of any other cause of the eosinophilia ([Caldwell, 2014](#)).

Eosinophilic gastritis and/or eosinophilic duodenitis (formerly referred to as eosinophilic gastroenteritis) represent what are traditionally believed to be rare types of EGID that are characterized by chronic, often severe inflammation due to patchy or diffuse infiltration of eosinophils into layers of the stomach, small intestine, or both the stomach and small intestine ([Prussin, 2014](#); [Reed, 2015](#); [Zhang, 2017](#)). The diagnosis is based on clinical presentation (gastrointestinal symptoms) combined with increased tissue eosinophils in biopsy specimens from the stomach and/or duodenum without any other cause for the eosinophilia. Involvement of the small intestine is typically assessed by performing duodenal biopsies using an esophago-gastro-duodenoscopy (EGD) and has been referred to as eosinophilic gastroenteritis or eosinophilic enteritis, though eosinophilic duodenitis is more appropriate. The gastrointestinal symptoms are believed to be due to the release of inflammatory mediators from activated eosinophils, and likely mast cells. Symptoms that are often severe and debilitating commonly include abdominal pain, nausea, bloating, early satiety, fullness before finishing a meal, abdominal cramping, vomiting, diarrhea, and weight loss ([Alhmoud, 2016](#); [Lopez-Medina, 2015](#); [Mansoor, 2017](#); [Reed, 2015](#)).

Jensen ([2016](#)) estimated the prevalence of EG and EoD to be 6.3/100,000 and 8.4/100,000 respectively (for patients ages 1–64 years old). Mansoor ([2017](#)) estimated the overall prevalence of EG to be 5.1/100,000 persons.

Patients may also have concomitant atopic diseases like food allergy, asthma, and atopic dermatitis, which further impact quality of life and contribute to health care costs. Additionally, 8% to 10% of patients have concomitant EoE ([Jensen, 2016](#)).

There are no FDA-approved treatments for EG and/or EoD. Current therapies and disease management include dietary restriction/elimination, proton pump inhibitors (PPI), antihistamines, systemic or topical corticosteroids, and occasional off-label use of immunomodulatory biologics (Prussin, 2014; Reed, 2015; Zhang, 2017). Proton pump inhibitors have little to no benefit in patients with EG and/or EoD despite reports of providing partial benefit in some patients with EoE (Katz, 2013). Restricted/elemental diets are not effective long-term treatment as they require strict compliance and, in the case of elemental diets, are expensive and are often not reimbursed by insurance. In addition, compliance is very poor, and patient quality of life is greatly impacted (Bedell, 2018; Peterson, 2013; Wechsler, 2014).

Corticosteroids, systemic or swallowed, have been shown to provide symptom relief but are not appropriate for long-term treatment due to numerous side effects and associated risks including adrenal insufficiency, bone demineralization, increased chance of infection, osteoporosis, behavioral issues, and weight gain.

By markedly reducing the number of blood and tissue eosinophils and inhibiting the activation of mast cells, AK002 may be useful in the treatment of patients with EG and/or EoD. This premise is supported by the Phase 2 data with AK002 that show significant improvement in histology and symptoms in these patients.

Given there are no approved therapies for these chronic and debilitating diseases, better treatment options are clearly needed to manage EG and EoD.

3. Rationale for Study and Dose Selection

Based on experience with AK002 in healthy volunteers and in patients with ISM, CU, severe AC, and EG/EoD, the proposed AK002 dose regimen of 18 total doses is 3 mg/kg administered every 4 weeks. To date, a range of AK002 doses from 0.0003 mg/kg to 10 mg/kg have been tested, and the maximum tolerated dose (MTD) has not been reached.

In the double-blind, placebo-controlled Phase 2 study in patients with EG and/or EoD, 2 dose levels were evaluated: a lower dose regimen (4 monthly doses of AK002 at 0.3, 1, 1, and 1 mg/kg) and a higher dose regimen (4 monthly doses of 0.3, 1, 3, and 3 mg/kg). Both regimens produced dramatic reduction in tissue eosinophils and were associated with substantial improvement in symptoms. However, numerically greater improvements were observed in the high dose arm compared with the low dose arm.

As there were no differences in safety or tolerability between the 2 dosing regimens and the higher regimen appeared to be more effective, the 3 mg/kg dose was selected for this Phase 3 open-label extension study.

The infusions were generally well tolerated at all doses with most IRR being mild to moderate and very few AE outside the infusion window. Patients with ISM, CU, severe AC, mast cell gastritis, and EG/EoD have received monthly doses of 1 mg/kg and 3 mg/kg AK002. Subsequent infusions in multiple dose cohorts were associated with fewer IRR when compared with the first infusion.

4. Study Objectives

The objective of the study is to generate open-label, longer-term safety, tolerability, and efficacy follow-up data in patients with EG and/or EoD who completed Study AK002-016 or Study AK002-012. In addition, this study provides patients randomized to placebo in AK002-016 the option to receive active dosing.

5. Study Design

5.1 Study Overview

This is a Phase 3, multicenter, open-label, extension study to evaluate the safety and tolerability of AK002 in patients with EG and/or EoD.

Patients who complete Study AK002-016 or Study AK002-012 will have the option to receive AK002 in an open-label manner. A patient is categorized as having completed Study AK002-016 if 6 infusions of study drug are administered and the patient is followed through at least Day 176 (± 3 days). A patient is categorized as having completed Study AK002-012 if the patient received all cohort-appropriate doses and was followed for 5 months after last dose of study drug in AK002-012. During Study AK002-016X, patients will maintain the same patient number that was assigned in Study AK002-016 or Study AK002-012, as applicable.

Safety will be assessed by body weight, vital signs, symptom-directed physical examination, complete blood count (CBC) with differential, blood chemistry, urinalysis, and assessment of AE including adverse events of special interest (AESI) and serious adverse events (SAE). In addition, blood samples will be obtained for evaluation of PK and ADA.

The study is designed as follows:

- Patients completing Study AK002-016 dosing and entering the extension study may begin extended dosing 1 day after the Day 176 visit of Study AK002-016, which will be considered Extension Day 1 of Study AK002-016X.

- Patients entering the extension study but who cannot start the extension study 1 day after the Day 176 visit has occurred will remain in the main study until they receive the first dose of study drug in the extension study.
- The Day 197 and Day 225 main study visits will occur if the patient does not enroll in the extension study prior to the scheduled date of these visits. A patient enrolling in the extension study prior to Day 197 will not complete the Day 197 or Day 225 procedures under the main study.
- A patient not enrolled in the extension study on or before Day 225 in the AK002-016 study will not be able to enter the extension study.
- Patients entering the extension study within 28 (± 3) days of the last study visit in AK002-016 will not require duplicate predose labs or procedures prior to the first dosing in AK002-016X.
- Patients will receive up to 18 infusions of AK002 administered every 28 (± 3) days in an open-label manner. All infusions of AK002 will be administered at 3 mg/kg.
- An EGD with biopsy will occur on Day 211 (± 3) and Day 505 (± 3) or 28 (± 3) days after last dose of study drug if early termination (ET).
- Patients will be followed for 84 (± 3) days after last dose. Follow-up safety visits will occur on Extension Days 512, 533, and 561 (± 3 days) or 35, 56, and 84 (± 3) days after last dose if ET from the study. If only 1 follow-up visit is possible, the EGD with biopsy and first safety follow-up visit (Day 35 after last dose) may be combined. If a patient does not agree to have the early-termination EGD, the first safety follow-up visit (Day 35 after last dose) should still occur.
- The extension study does not include fasting requirements, except for those required for the conduct of EGD. Patients underwent a standardized baseline evaluation of eating habits, food habits/restrictions, and food avoidance behaviors during Study AK002-016 and will be asked to maintain the same diet through the first 6 months of the study. After the seventh dose has been received, diet and eating habits may be liberalized, as desired, with all changes that occur noted in the CRF.
- Prestudy medications should remain unchanged throughout the study. Systemic or swallowed steroids above 10 mg daily prednisone (or equivalent) will not be allowed except as an approved premedication prior to infusion, to treat an IRR that occurs during infusion, or the use is due to unforeseen circumstances when it is deemed medically necessary to treat an unrelated medical condition.

- Daily administration of the PRO questionnaire (including any appropriate additional questions) throughout the study and the follow-up period for all patients.
- Total duration of Study AK002-016X will be approximately 21 months.

5.2 Schedule of Events

The overall schedule of procedures and assessments are depicted in [Table 1](#).

Table 1 Schedule of Assessments

		Extension Treatment Period (18 months)				Extension Follow-Up Period (12 weeks)				
		Dose 1	Doses 2-7	Dose 8	Day 211	Doses 9-18	EGD	Follow-up #1	Follow-up #2	Follow-up #3
Prior to First Dose	Assessments	Extension Day 1 85, 113, 141, 169 (± 3 days)	Day 29, 57, 85, 113, 141, 169 (± 3 days)	Day 197 (± 3 days)	(± 3 days)	Day 225, 253, 281, 309, 337, 365, 393, 421, 449, 477 (± 3 days)	Day 505 (± 3 days) or 28 days after last dose if ET	Day 512 (± 3 days) or 35 days after last dose if ET	Day 533 (± 3 days) or 56 days after last dose if ET	Day 561 (± 3 days) or 84 days after last dose if ET
Informed consent	X									
Medical History ¹	X									
Prior/Concomitant Medications ²	X ³	X	X	X	X	X	X	X	X	X
Baseline Diet Assessment/Compliance	X ³	X	X	X	X	X	X	X	X	X
Body weight ⁴	X(predose) ³	X(predose)	X(predose)	X(predose)	X(predose)	X(predose)	X	X	X	X
Vital signs ⁵	X	X	X	X	X	X	X	X	X	X
Symptom-directed Physical Exam ⁶	X ³	X	X	X	X	X	X	X	X	X
Eligibility assessment	X	X								
ePRO Training and Activation ⁷	X									
ePRO Questionnaire (may include additional questions) ⁸										
SF-36 Health Survey ⁹		X ³	X	X	X	X	X	X	X	X
Dysphagia Question										
Dipstick Pregnancy Test ¹⁰	X ³ (predose)	X(predose)	X(predose)	X(predose)	X(predose)	X(predose)	X			
Access IRT to enter Patient ID and current body weight ¹¹	X(predose)	X(predose)	X(predose)	X(predose)	X(predose)	X(predose)				
Premedication: prednisone ¹²	X ²¹									
Study drug administration ¹³	X ²²	X	X	X	X	X	X	X	X	X

<-----Perform daily from Day 1 through Day 561 or 84 days after last dose, if ET----->
 <-----Perform daily from Day 1 through Day 561 or 84 days after last dose, if ET----->

Table 1 Schedule of Assessments cont.

Assessments	Prior to First Dose	Extension Treatment Period (18 months)				Extension Follow-Up Period (12 weeks)			
		Dose 1	Doses 2-7	Dose 8	Day 211	Doses 9-18	EGD Follow-up	Follow-up #1	Follow-up #2
Blood for CBC with differential ^{14,15}	X	X	X	X	X	X	X	X	X
Blood for chemistry ^{14,16}	X (predose) ³	X (predose)	X (predose)	X (predose)	X (predose)	X (predose)	X	X	X
Urinalysis ^{14,17}	X (predose) ³	X (predose)	X (predose)	X (predose)	X (predose)	X (predose)	X	X	X
Blood for pharmacokinetics ^{14,18}	X (predose) ³	X (predose)	X (predose)	X (predose)	X (predose)	X (predose)	X	X	X
Blood for ADA ^{14,19}	X (predose) ³	X (predose)	X (predose)	X (predose)	X (predose)	X (predose)	X	X	X
Blood for Total Serum IgE ^{14,20}	X (predose) ³						X	X	X
EGD with biopsy ²³					X		X	X	X
Non-serious adverse events ²⁴	X	X	X	X	X	X	X	X	X
Adverse events of special interest ²⁵	X	X	X	X	X	X	X	X	X
Serious adverse events ²⁶	X	X	X	X	X	X	X	X	X

CBC: Complete Blood Count

EGD: Esophago-Gastro-Duodenoscopy

ET: Early Termination

IRT: Interactive Response Technology

Table Notes

- 1) Record all pertinent, ongoing medical history as well as any significant adverse events (AE) that occurred in the AK002-016 or AK002-012 study but resolved before the first dose in the extension study.
- 2) Record all concomitant medications taken within 30 days of Extension Day 1 and during the course of the study. Record all concomitant medication received during EGD, any premedication given, and any medication used for the treatment of IRR.
- 3) Do not collect if procedure was performed as part of the last study visit in AK002-016 (on Day 176, 197 or 225, depending on when patient receives first dose in AK002-016X). Differential cell counts collected for Study AK002-016X postdose CBC with differential is still required 1 hour (± 15 minutes) after the first AK002-016X infusion ends.

Table Notes cont.

- 4) Body weight will be measured predose and recorded in kilograms (kg) on Day 1, all infusion days, and at Follow-up visits on Days 512, 533, and 561 or 35 (± 3), 56 (± 3), and 84 (± 3) days after last dose of study drug if ET. Body weight is to be measured in kg as it is used to determine patient dosing calculations
- 5) Vital signs including systolic and diastolic blood pressure, pulse, body temperature, and respiratory rate will be taken after the patient has been at rest for ≥ 5 minutes and before any blood draw. Vital signs will be measured on all dosing days within 30 minutes predose, within 30 minutes after the start of infusion, and within 30 minutes following the end of infusion.
- 6) A symptom-directed physical examination (including assessment of possible infusion site reactions) will be performed by the Investigator or designee, as needed if any significant symptoms or changes from baseline are reported.
- 7) Activate PRO questionnaire and provide patient with unique username and password. Use ePRO Teaching Tool for patient training and reference. PRO questionnaire should be activated for all patients on Day 1.
- 8) The PRO should be completed by the patient, around the same time each day using ViedocME electronic portal. Patients with concomitant history of asthma and/or atopic dermatitis symptoms will receive an extra question about each, as appropriate. If the dysphagia question was populated in AK002-016, it will continue to populate in the daily ViedocME questions for AK002-016X. The PRO may be completed via paper if electronic access is not possible.
- 9) Completed in clinic by the patient (complete prior to blood draw, physical examination, or vital sign measurements) during study visits, using ViedocME electronic portal. May be completed via paper if electronic access is not possible.
- 10) A small amount of urine collected for urinalysis will be used for dipstick pregnancy test (for women of childbearing ability) predose on all infusion days and on Day 512 (± 3) or 35 (± 3) days after last dose if ET. Test kits will be supplied by the central laboratory. Tests will be completed on site and evaluated prior to infusion.
- 11) Endpoint IRT to be used to assign kit numbers for each patient dosing. Current patient body weight (taken day before infusion or day of infusion) will be entered into IRT and amount of AK002 to be mixed with 0.9% NaCl will be calculated via Endpoint.
- 12) All patients will self-administer 80 mg oral prednisone 12–24 hours prior to the first infusion. An approved alternative(s) may be used with the approval of the Medical Monitor. Premedication may be administered prior to subsequent infusions at the Investigator's discretion, but only with written approval from the Medical Monitor.
- 13) Study drug will be administered as a single peripheral IV infusion over at least a 4-hour period for Dose 1. Second and subsequent infusions can be given over at least a 2-hour period, depending on prior infusion tolerability. After the sixth infusion a 1-hour infusion schedule may be used. Refer to the Pharmacy Manual.
- 14) Specimen processed by central laboratory. See central laboratory manual for collection and processing details.
- 15) Blood for CBC with differential, including absolute blood eosinophil count, will be obtained just prior to each infusion, 1 hour (± 15 minutes) after the end of each infusion as well as on Extension Days 512, 533, and 561 (± 3 days) or 35, 56, and 84 (± 3) days after last dose of study drug if ET.
- 16) Blood for Chemistry will be obtained just prior to each infusion as well as on Extension Days 512, 533, and 561 (± 3) or 35, 56, and 84 (± 3) days after last dose of study drug if ET.
- 17) Urine for Urinalysis will be collected on Extension Days 1, 197 (± 3), and 512 (± 3) or 35 (± 3) days after last dose of study drug if ET.

Table Notes cont.

- 18) Blood for PK will be collected on Extension Days 1, 197 (± 3), and 512 (± 3) or 35 (± 3) days after last dose of study drug if ET.
- 19) Blood for ADA will be collected on Extension Days 1, 197 (± 3), and 512 (± 3) or 35 (± 3) days after last dose of study drug if ET. ADA will also be collected when an immunogenicity-related AE occurs.
- 20) Blood for Total Serum IgE will be collected on Extension Day 1 and Extension Day 512 (± 3) or 35 (± 3) days after last dose of study drug if ET.
- 21) The consent form for AK002-016X must be signed *prior* to the patient taking prednisone premedication for the AK002-016X study.
- 22) The final EGD and Day 176 hematology assessment (first safety follow-up) for AK002-016 *must* be collected *prior* to the patient taking prednisone premedication for AK002-016X. Therefore, dosing in AK002-016X must take place at least 1 day after completion of the Day 176 visit for AK002-016.
- 23) See [Appendix 6](#) for biopsy assessments. EGD should occur on Day 211 (± 3) and Day 505 (± 3) or 28 (± 3) days after last dose of study drug if the patient discontinues the study early and agrees to have an early termination biopsy.
- 24) Non-serious AE will be captured from Day 1 (first dose of study drug) through Day 561 (± 3) or 84 (± 3) days after last dose of study drug if ET.
- 25) Adverse events of special interest will be captured from Day 1 (first dose of study drug) through Day 561 (± 3) or 84 (± 3) days after last dose of study drug if ET.
- 26) Serious adverse events will be captured from Day 1 (first dose of study drug) through Day 561 (± 3) or 84 (± 3) days after last dose of study drug if ET.

6. Criteria for Evaluation

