9.5 Preparation of Study Drug

A study pharmacist or designee will prepare the study drug for each infusion. Based on patient body weight obtained the day of or the day prior to dosing, the designated study pharmacist will prepare the appropriate dilution of AK002 for intravenous administration.

Appropriate aseptic technique will be used, and the drug will be prepared according to the pharmacy manual for AK002. Refer to the Pharmacy Manual for additional details and step-by-step instructions regarding study drug preparation.

The infusion must be completed within 8 hours of preparation. Preparation is when AK002 is first mixed with NaCl.

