11.3.2 Body Weight

Body weight will be measured predose and used to determine the amount of study drug to be mixed with NaCl for each infusion. Body weight must be measured on the day of, or on the day prior to, the day of each infusion. Body weight will be entered into the interactive response technology (IRT) system for each dosing visit and will also be recorded on the Investigational Product Dose Calculation and Preparation Worksheet that the pharmacist or designee will maintain to document each patient's dose calculations.

Body weight should be collected on site on the day of each study drug infusion or on the day prior to each infusion. Body weight will also be captured on Days 512, 533, and 561 (± 3) or 35, 56, and 84 (± 3) days after last dose of study drug if ET.

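### Table 1 note 3 tells sites to skip the Extension Day 1 body weight if it was taken at the last AK002-016 visit, contradicting the protocol's rules for the weight used to calculate Dose 1

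*Combined protocol and SAP*

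**What the plan says.** Two sets of instructions in the protocol bear on the Extension Day 1 weight.

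**Text that drops the measurement**
- Table 1 (Section 5.2) puts superscript 3 on the first predose cell of the Body weight row. Note 3 reads "Do not collect if procedure was performed as part of the last study visit in AK002-016" and identifies that visit as "on Day 176, 197 or 225, depending on when patient receives first dose in AK002-016X". It sets no limit on the age of the earlier value and makes no exception for weight.
- Section 5.1, like the synopsis, sets a window of 28 (± 3) days counted from that visit. Of patients who enter inside the window it says that they "will not require duplicate predose labs or procedures prior to the first dosing in AK002-016X". Weight is not excepted here either.

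**Text that requires it**
- Table 1 note 4, on the same row: "Body weight will be measured predose and recorded in kilograms (kg) on Day 1, all infusion days". The note adds that weight determines the dose.
- Table 1 note 11: the weight entered in the IRT, from which the amount of AK002 is calculated, comes from the infusion day or the day before.
- Section 9.4: the amount is worked out before each infusion from current weight.
- Section 9.5: the dilution is prepared "Based on patient body weight obtained the day of or the day prior to dosing".
- Section 11.3.2: "Body weight must be measured on the day of, or on the day prior to, the day of each infusion".
- Section 12.2: weight is to be determined on Extension Day 1, and Dose 1 is prepared from a weight taken then or the day before. Other items in the same list may be carried over from AK002-016; weight may not.

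**The concern.** Every infusion is 3 mg/kg, so any error in the weight passes straight through to the dose. Note 3 is worded as an instruction not to collect, and Sections 11 and 12 both send sites to Table 1 for what to do at each visit. A site cannot obey note 3 and also Sections 9.5, 11.3.2 and 12.2 when the last AK002-016 visit was more than a day earlier, so either choice departs from some protocol text.

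Dose 1 is also the first AK002 exposure for patients randomized to placebo in AK002-016. Section 3 reports fewer infusion-related reactions at later infusions than at the first. That is a reason for the Dose 1 instruction to be unambiguous. It is not evidence that a small weight error would cause a reaction.

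**Working it through.** The plan gives no figure for the age of a carried-over weight, so there is none to reproduce. The check is a cross-reading, some date arithmetic and one illustration of dose.

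**1. Is the marker on the Day 1 weight?** Table 1 lost its column alignment when it was read from PDF, so position alone does not settle this. Three things support it.
- The Vital signs row has no superscript 3, so the marker is selective.
- The serum IgE row carries the same marker on its first cell, and note 20 limits IgE to Day 1 and Day 512 (or 35 days after the last dose on early termination). The first marked cell is therefore the Day 1 collection.
- Section 12.1 schedules no weighing before Day 1.

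**2. Is weight treated like the other rows marked with note 3?**

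| Marked item | Carry-over in the procedure text? |
|---|---|
| SF-36, diet, physical examination, chemistry, IgE, ADA, PK, urinalysis, pregnancy test | Yes, Section 12.2 |
| Concomitant medications | Yes, Section 11.3.1 |
| Body weight | No; Sections 9.5, 11.3.2 and 12.2 require a weight from the infusion day or the day before |

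Weight is the one marked row that the procedure text contradicts.

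**3. How old could a carried-over weight be?** Inputs from Section 5.1: AK002-016 visits at Days 176, 197 and 225; the Day 197 and 225 visits take place only if the patient has not entered the extension before they are due; entry closes after Day 225; the waiver runs to 28 (± 3) days.
- Last visit Day 176, first dose Day 196: 196 − 176 = 20 days.
- Last visit Day 197, first dose Day 224: 224 − 197 = 27 days.
- Full gap between the last two visits, also the nominal waiver limit: 225 − 197 = 28 days.
- Waiver at its limit: 28 + 3 = 31 days. Section 12.2 uses 28 days without the extra 3 for the items it lets sites carry over.
- Under note 11 and Sections 9.5, 11.3.2 and 12.2: at most 1 day.

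If Dose 1 follows the Day 176 visit by one day, the earliest start allowed, that visit's weight already satisfies the day-before rule and there is no conflict.

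**4. What would the dose error be?** The documents give no data on weight change. Assume a carried-over weight of 70 kg and a true change of 2% to 5%.
- Dose from the carried-over weight: 3 × 70 = 210 mg.
- 2%: 0.02 × 70 = 1.4 kg, and 3 × 1.4 = 4.2 mg.
- 5%: 0.05 × 70 = 3.5 kg, and 3 × 3.5 = 10.5 mg.
- Dose per current kg = 3 / (1 + fractional change):

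| Assumed change since last visit | Dose per current kg (mg/kg) |
|---|---|
| −5% | 3 / 0.95 = 3.16 |
| −2% | 3 / 0.98 = 3.06 |
| +2% | 3 / 1.02 = 2.94 |
| +5% | 3 / 1.05 = 2.86 |

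**The case against.** The strongest reply is that the protocol, read as a whole, forbids dosing on an old weight. The IRT entry has its own row in Table 1, which carries note 11 and not note 3. A site that reads that row is told to enter a weight from the infusion day or the day before. Note 4 sits on the Body weight row itself, and Sections 9.4, 9.5, 11.3.2 and 12.2 all point the same way. The waiver in Section 5.1 only says that repeats are not required; it does not forbid weighing. This stands. A reader might infer from note 3 that sites would dose on a month-old weight, or that the protocol tells them to. The documents support only that a site could do so if it followed note 3 over the other text.

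A reader might also infer that the Day 1 weight is the reference for change in body weight, so that skipping it would damage a safety endpoint. Section 6.1 lists changes in body weight but names no baseline. Section 15.3 lists only Day 1 vital signs and laboratory tests, and Section 11.3.4 does not include weight among the vital signs. That inference is not supported.

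It is fair, too, that Table 1 is damaged in the text available, that the weight changes are assumed, and that Section 3 reports doses up to 10 mg/kg without a maximum tolerated dose being reached. These points limit the size of the concern. They do not remove the conflict between note 3 and note 4, which are attached to the same row.

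**Conclusion.** The point holds as an internal contradiction in the schedule that feeds a weight-based dose. Note 3 and the waiver allow the Day 1 weight to be left out; notes 4 and 11 and Sections 9.4, 9.5, 11.3.2 and 12.2 do not.

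The effect is confined to Dose 1 of AK002-016 entrants who are not dosed within a day of their last visit in that study. Note 3 does not mention AK002-012 entrants, and the documents do not say how many patients fall in the affected group. The likely dose error is modest: 2% to 5% under the stated assumption. The conclusion does not depend on that assumption, but it does rest on reading the marked cell as the Day 1 entry, which the IgE row and note 20 support. The correction is worth making because it is specific and costs very little.

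**What to change.** The sponsor should reconcile the Body weight marker in Table 1, note 3 and the waiver in Section 5.1 and the synopsis with notes 4 and 11 and Sections 9.4, 9.5, 11.3.2 and 12.2, so that sites have one consistent instruction for the weight used to calculate Dose 1. Which rule applies is for the sponsor to decide, and the dose level is not in question. The cost is a short correction to the table, its note and the waiver sentence, or to the sections that conflict with them. If the sponsor settles on a Day 1 weighing, the added burden is one measurement at a visit the patient attends anyway.
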